6.2.1.5 Retreatment Group

Subjects who have derived sustained benefit from treatment, meaning at least stable disease and no worsening of performance status, for at least 3 months after the end of treatment but experience relapse or progression thereafter, and have not received any other systemic anti-cancer therapy since their last AMG 910 treatment, may be retreated in a separate retreatment group for a total of up to 2 rounds of retreatment (**up to 6 cycles each**). Retreatment will be offered to such subjects upon agreement of the investigator and the Amgen Medical Monitor that retreatment is medically appropriate and likely to provide benefit for the subject. Subjects must meet all protocol defined inclusion and exclusion criteria and provide written consent for the retreatment (exemption: no additional test for CLDN18.2 expression in tumor tissue is required). Retreatment will be administered at the highest dose level and currently used schedule that has been assessed as safe by the DLRT at the time of retreatment initiation. Treatment schedule and schedule of activities will be conducted as described for cycles 1 through 6 in the dose exploration and expansion cohorts.

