- Retention of study documents will be governed by the Clinical Trial Agreement.

Study and Site Closure

Amgen or its designee may stop the study or study site participation in the study for medical, safety, regulatory, administrative, or other reasons consistent with applicable laws, regulations, and GCP.

Both Amgen and the Investigator reserve the right to terminate the Investigator's participation in the study according to the Clinical Trial Agreement. The investigator is to notify the IRB/IEC in writing of the study's completion or early termination and send a copy of the notification to Amgen.

Subjects may be eligible for continued treatment with Amgen investigational product(s) by an extension protocol or as provided for by the local country's regulatory mechanism. However, Amgen reserves the unilateral right, at its sole discretion, to determine whether to supply Amgen investigational product(s) and by what mechanism, after termination of the study and before the product(s) is/are available commercially.

Compensation

Any arrangements for compensation to subjects for injury or illness that arises in the study are described in the Compensation for Injury section of the Informed Consent that is available as a separate document.

11.4 Appendix 4. Safety Events: Definitions and Procedures for Recording, Evaluating, Follow-up, and Reporting

Definition of Adverse Event

Adverse Event Definition

• An adverse event is any untoward medical occurrence in a clinical study subject irrespective of a causal relationship with the study treatment.• Note: An adverse event can therefore be any unfavorable and unintended sign (including an abnormal laboratory finding), symptom, or disease (new or exacerbated) temporally associated with the use of a treatment, combination product, medical device or procedure.• Note: Treatment-emergent adverse events will be defined in the SAP.

Events Meeting the Adverse Event Definition

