3.1.4 Re-treatment of Subjects

Subjects who have derived sustained benefit from treatment, meaning at least stable disease and no worsening of performance status, for at least 3 months after the end of treatment but experience relapse or progression thereafter, and have not received any other systemic anti-cancer therapy since their last AMG 910 treatment, may be retreated in a separate retreatment group **for a total of up to 2 rounds of retreatment (up to 6 cycles each)**. Retreatment will be administered at the highest dose level and currently used schedule that has been assessed as safe by the DLRT at the time of retreatment

initiation. Treatment schedule and schedule of activities will be conducted as described for cycles 1 through 6 in the dose exploration and expansion cohorts.

Figure 3-1. Study Schema

LTFU = long-term follow-up; MTD = maximum tolerated dose; RP2D = recommended phase 2 dose

SFU = safety follow-up

^a Multiple-subject cohorts will enroll at a dose level where specific safety and/or efficacy criteria were met in a single-subject cohort or per planned dose level from [Table 3-1](#). For subsequent dose level cohorts, 3-4 total subjects will be enrolled.

^b For cohorts 1b onwards, AMG 910 is administered as extended IV infusion over 96 hours in cycle 1 week 1 and as short-term IV infusions weekly (or twice weekly) starting cycle 1 day 8 onwards in cycle 1 through 6 of 28-day cycles with scheduled 2-week breaks after cycles 2 and 4.

Table 3-1. Planned Doses per Dose Cohort Level

Cohort number	Number of subjects ^a	Dose (µg) Route
(-1)	(3 to 4)	2.5 IV
1	3 to 4	6.5^b IV
1b	3 to 4	6.5^b eIV
2b	3 to 4	15 eIV
3b	3 to 4	30 eIV
4b	3 to 4	60 eIV
5b	3 to 4	150 eIV
6b	3 to 4	300 eIV
7b	3 to 4	600 eIV
8b	3 to 4	1000 eIV
9b	3 to 4	2000 eIV

Routes of administration: eIV = extended intravenous; IV = short-term intravenous.

^a Switching from a single subject cohort to a multiple-subject cohort will occur with cohort 3 or sooner if specific safety criteria are observed as described in Section 6.2.1.1.1 in the protocol.

^b If a dose reduction is needed according to instructions provided in Table 6-3 as in the protocol, treatment will be continued at a dose of 2.5 µg as specified in Section 6.2.2.3.5 as in the protocol.

Note: The “b” cohort numbers are used to differentiate cohorts 1 through 10 denoted in previous versions of the protocol

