Body Mass Index should be calculated using the following formula:

$$\text{BMI (kg/m}^2\text{)} = \text{weight (kg)} / [\text{height (cm)} / 100]^2$$

Change from Baseline

Change from Baseline is the arithmetic difference between post-dose assessments and Baseline value.

$$\text{Change (absolute) from Baseline} = (\text{Post-baseline Value} - \text{Baseline Value})$$

$$\text{Change (percent) from Baseline} = [(\text{Post-baseline Value} - \text{Baseline Value}) / \text{Baseline Value}] \times 100$$

C}_{\text{max}}

Maximum observed drug concentration.

C}_{\text{min}}

Minimum observed drug concentration.

Dose Limiting Toxicity

Dose limiting toxicities are defined as any adverse events at least possibly related to AMG 910 with an onset within the first 28 days following first dose for single-subject cohorts and within the safety observation period for multiple-subject cohorts as defined in section 6.2.1.1.3 of the protocol.

Additional information on DLTs are given in the section 6.2.1.1.2 of the protocol.

End of study (End of trial)

It is defined as the date when the last subject across all sites is assessed or receives an intervention for evaluation in the study (i.e., last subject last visit), following any additional parts in the study (e.g., long-term follow-up), as applicable.

Fridericia-corrected QT intervals (QTcF)

The Fridericia correction will be calculated from the investigator reported QT (msec) and RR interval (msec), as follows:

$$\text{QTcF} = \text{QT}/(\text{RR}/1000)^{1/3}$$

Investigational product (IP)

The term 'investigational product' is used in reference to AMG 910.

Last investigational product dose date

The last IP date for each subject is defined as the latest date IP administered.

Long term follow-up (LTFU)

Subjects will be followed for every 6 months up to 2 years from the first dose of AMG 910 for all subjects who have not withdrawn consent by clinic visit, telephone or chart review to assess for survival and/or the commencement of subsequent cancer therapy. **Subjects who remain on the treatment for more than 2 years do not need to have additional long-term follow-up (LTFU). They will complete the study 30 (+3) days following discontinuing treatment.**

Maximum Tolerated Dose (MTD)

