A final estimate of the MTD will be made based on a Bayesian Logistic Regression Model (BLRM) utilizing all DLT-evaluable subjects from the dose exploration and dose expansion cohorts. The MTD for BLM is the dose level predicted to have the highest probability of a DLT rate within the target interval of 20% to 33%, subject to overdose control. To control the risk of overdose, the MTD must have less than a 40% predicted probability of overdosing (DLT rate >33%).

Primary completion

The primary completion date is the date when data for the primary endpoint are last collected for the purposes of conducting the primary analysis. It is the date when the last subject is assessed or receives AMG 910 for the final collection of data for the primary endpoint(s), for the purposes of conducting the primary analysis, whether the study concluded as planned or was terminated early.

Safety follow-up

It is defined as the subject visit at least 30 (+3) days after last dose of AMG 910 is received to assess the risk of delayed adverse events.

Serious adverse event

A Serious Adverse Event is defined as any untoward medical occurrence that, meets at least 1 of the following serious criteria:

- Results in death (fatal).
- Immediately life-threatening.
- Requires in-patient hospitalization or prolongation of existing hospitalization.
- Results in persistent or significant disability/incapacity.
- Other medically important serious event.
- Is a congenital anomaly/birth defect.

Study day

Post-study day: study day= (date – date of Study Day 1) + 1.

Pre-study day: study day= (date – date of Study Day 1).

Study day 1

It is defined as the first day that AMG 910 is administered to the subject.

Treatment emergent adverse event

A treatment - emergent adverse event (**TEAE**) is any adverse event starting on or after the first administration of investigational product, as determined by the flag indicating if the adverse event started prior to the first dose on the Events CRF, and up to and including 30 days after the last IP dose date. The severity of each adverse event will be graded using the CTCAE version 5.0. Adverse events will be coded using MedDRA.

Treatment related adverse event

A treatment-related AE is any treatment-emergent AE that per investigator review has a reasonable possibility of being caused by AMG 910.

6. Analysis Sets

The following sub-sections describe the analysis sets to be used.

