9.6.2 Adverse Events

The Medical Dictionary for Regulatory Activities (MedDRA) version [25.0] or later will be used to code all events categorized as adverse events to a system organ class and a preferred term.

Subject incidence of all treatment-emergent adverse events, serious adverse events, adverse events leading to **drug interruption**, withdrawal of investigational product, fatal adverse events and subject incidence of AEs by PT will be listed, summarized and tabulated by system organ class and preferred term in decreasing frequency order.

Summaries of treatment-emergent, serious adverse events will be tabulated by system organ class, preferred term, grade (3 or higher) and dose/cohort.

In addition, separate descriptive tables will be tabulated for all treatment emergent AE, all treatment related AEs, all serious AEs, related serious AEs, treatment emergent AEs

by grade, all fatal AEs, will be tabulated and presented by cohort and dose. **Partial / missing date imputation rules are given in [Appendix A](#).**

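### The SAP's single treatment-emergent window spans a retreated subject's off-drug months, and no rule says where retreatment events are tabulated.

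*SAP*

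**What the plan says.** The protocol leaves the definition to the SAP: Appendix 4 (11.4) notes that "Treatment-emergent adverse events will be defined in the SAP". SAP Section 5 starts the window at the first administration and runs it "up to and including 30 days after the last IP dose date". It fixes the end point as follows: "The last IP date for each subject is defined as the latest date IP administered". Neither definition is limited to the initial course.

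Retreatment is provided for in both documents. Under SAP 3.1.4 a subject qualifies after benefit lasting "for at least 3 months after the end of treatment but experience relapse or progression thereafter". Protocol 6.2.1.5 says such a subject "may be retreated in a separate retreatment group for a total of up to 2 rounds of retreatment", each of up to 6 cycles. On dose, SAP 3.1.4 says: "Retreatment will be administered at the highest dose level and currently used schedule that has been assessed as safe by the DLRT".

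SAP 6.1 defines one safety set of all treated subjects. Under SAP 9.6.2 the separate adverse event tables "will be tabulated and presented by cohort and dose". SAP 9.6.6 summarises maximum ECG change and maximum post-baseline ECG values by cohort. No analysis set, window or table in the SAP is specific to retreatment.

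**The concern.** Two things go wrong when these definitions meet a retreated subject.

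First, the window does not close after the initial course. Months without drug, ending in relapse, become treatment-emergent time. Protocol 8.2.4.1.2 has sites report serious events through long-term follow-up or end of study, and Appendix 4 asks for the signs and symptoms of adverse events caused by the cancer. Serious complications of relapse can therefore enter the treatment-emergent tables although no drug was being given.

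Second, the plan cannot be programmed for a subject who has received two doses without a choice that it does not state. Safety and tolerability and determination of the MTD or RP2D are the primary objectives, the escalation cohorts hold 3 to 4 subjects, and the adverse event tables are read by dose. One subject's retreatment events in the wrong column can change that column visibly.

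**Working it through.** The documents give no figure to reproduce, so the definitions are applied to an illustrative subject.

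**Inputs**
- Six 28-day cycles with 2-week breaks after cycles 2 and 4 (Protocol 4.1).
- Last weekly dose on cycle 6 day 22 (Protocol Table 1-1).
- 30-day tail (SAP 5).
- At least 3 months off treatment before retreatment (SAP 3.1.4).
- Assumptions: all cycles are given on schedule, and 3 months is 91 days.

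**Window if it closed after the initial course**
- Course length: 6 × 28 + 2 × 14 = 196 days.
- Day of last dose: 196 − 28 + 22 = 190.
- Window end: 190 + 30 = day 220.

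**Window as written, with one full retreatment round**

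| 3 months counted from | Earliest restart | Off-drug days after day 220 | Last retreatment dose | Window end |
|---|---|---|---|---|
| Last dose (day 190) | 190 + 91 = 281 | 221 to 280 = 60 | 280 + 190 = 470 | 500 |
| End-of-treatment visit (day 196) | 196 + 91 = 287 | 221 to 286 = 66 | 286 + 190 = 476 | 506 |

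The window ends on day 500 to 506 instead of day 220. At least 60 to 66 of the added days are off drug. Two gaps of minimum length give 120 to 132 such days.

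**What is collected in the gap.** Protocol 8.2.4.1.1 collects adverse events through safety follow-up, 30 (+3) days after the last dose. Protocol 8.2.4.1.2 continues serious events to long-term follow-up or end of study. The gap therefore adds mainly serious events. The protocol does not say whether the last dose in 8.2.4.1.1 means that of the initial course.

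**How far the dose can differ.** Planned targets in SAP Table 3-1 for the eIV cohorts are 6.5, 15, 30, 60, 150, 300, 600, 1000 and 2000 µg. Adjacent levels differ by a factor of 1.67 (1000/600) to 2.5 (150/60). The full ladder spans 2000/6.5 = 308-fold, which is the arithmetic limit and not an expected case.

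**Effect of one subject on an incidence.** 1/4 = 25 and 1/3 = 33 percentage points. This is an upper bound: it requires that the subject did not already have that event in the initial course.

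**The case against.** The strongest reply is that the SAP nowhere assigns retreatment events to the original cohort. A reader might infer that it does, but SAP 3.1.4 says subjects "may be retreated in a separate retreatment group", and tables by cohort and dose could equally be built on the retreatment dose. That stands: attribution is unspecified. Original-cohort pooling is still the likely default. The subject number never changes (Protocol 5.3), there is one safety set, SAP 6.3.1 speaks of a single dose level cohort per subject, and ECG maxima are summarised by cohort.

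Other stronger readings also fail.
- **Laboratory maxima.** SAP 9.6.3 plans values or changes at scheduled assessments and grade shifts. Only ECG has a maximum post-baseline summary.
- **One-way bias.** It is tempting to say that high-dose events would always appear under low doses. A subject first treated at a dose later judged too toxic could be retreated lower, and an expansion subject could be retreated at the same dose. Protocol 6.2.1.1.1 also expects little activity at the first 3 to 4 levels, so the widest dose jumps are the least likely.
- **DLT, BLRM and best response.** The DLT window is tied to the first dose or the cohort's safety observation period, so an event in retreatment months later falls outside it. Protocol 8.2.2 ends RECIST 1.1 assessment at first progression, and SAP 9.5.2 analyses response by RECIST 1.1 only.

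Two further points limit the effect. Gap events judged unrelated stay out of the treatment-related tables. Retreatment is optional and needs renewed consent, eligibility and medical agreement, and SAP 7.1 records early termination, so few or no subjects may have been retreated. Neither point closes the window or supplies the missing rule.

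**Conclusion.** The concern holds in two parts. The first follows from the SAP's own words: one window per subject, running to the latest dose on any date, makes at least about 60 off-drug days per gap treatment-emergent in a retreated subject, with mainly serious events affected. The second is an omission: the SAP does not say where adverse events and ECG maxima from a retreatment course are counted. If they are pooled under the original cohort, which is likely but not stated, an incidence in a cohort of 3 to 4 could move by up to 25 to 33 points.

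The day count assumes a full initial course, on-time weekly dosing in cycle 6 and the shortest permitted gap. The documents do not give the number retreated, so the actual effect ranges from nil upwards. The documents do not support a claim that dose-toxicity is systematically flattened or that the MTD estimate is biased.

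**What to change.** In SAP 5, end the treatment-emergent window 30 days after the last dose of each treatment course, and give each retreatment round its own window starting at its first dose.

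In SAP 9.6, restrict the cohort and dose adverse event tables and the ECG maximum summaries to the initial course. List or tabulate retreatment events separately, by the dose actually given.

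If nobody was retreated, one sentence saying so is enough.

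The cost is SAP wording and one course flag in the analysis datasets. Dose amounts and infusion times are already recorded on the CRF (Protocol Table 6-1 and 6.4), so no new data are needed. The trade-off is that the initial-course tables will no longer include retreatment events, so a reader who wants all exposure must use both displays.

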Routine radiological imaging (contrast-enhanced CT scans) and tumor burden assessments will be performed as outlined in the Schedule of Activities. Assessment of disease response will be determined based on RECIST 1.1 and iRECIST guidelines.

To further assess the risk of delayed adverse events, the subject must return for a safety follow-up visit at least 30 (+3) days after the last dose of AMG 910. Long-term follow-up will be conducted every 6 months up to 2 years from the first dose of AMG 910 by clinic visit, telephone, chart review or by access of public databases to assess for survival, serious adverse events, and/or the commencement of subsequent cancer therapy for all subjects who have not withdrawn consent. **Subjects who remain on the treatment for more than 2 years do not need to have additional long-term follow-up. They will complete the study 30 (+3) days following discontinuing treatment.**

For a full list of study procedures, including the timing of each procedure, please refer to Section 8.2 and the Schedule of Activities in [Table 1-1](#).

Statistical Considerations

All subjects who are enrolled and receive at least 1 dose of AMG 910 will be included in the analysis, unless otherwise specified. A formal interim analysis of available safety and efficacy data will occur when all dose-escalation subjects have had the opportunity to complete 28 days on study. This interim analysis will estimate the MTD, support the determination of the RP2D, and support the evaluation of the benefit/risk profile of AMG 910.

The primary analysis for the safety endpoints, PK endpoints, and objective response endpoints will occur when enrollment is complete, and each subject has had the opportunity to receive at least 6 cycles of treatment. The primary analysis for time to event endpoints will occur when enrollment is complete, and each subject has had the opportunity to be on the study for at least 2 years. The final analysis will occur when target enrollment is complete for both phases and all subjects have ended the study.

For a full description of statistical analysis methods, please refer to Section 9.

[figure not shown]
Statistical Hypotheses

AMG 910 will demonstrate acceptable safety and tolerability in subjects with gastric or GEJ adenocarcinoma at 1 or more dose levels with at least 1 dose level showing evidence of anti-tumor activity.

Sponsor Name: Amgen Inc.

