8.2.4 Adverse Events and Serious Adverse Events

8.2.4.1 Time Period and Frequency for Collecting and Reporting Safety Event Information

8.2.4.1.1 Adverse Events

The adverse event grading scale to be used for this study will be the Common Terminology Criteria for Adverse Events (CTCAE) version 5.0 and is described in Section 11.14, with the exception of CRS, which will be graded using the criteria referenced in the publication by Lee et al (2014) (see Section 11.13) and TLS, which will be graded according to the Cairo Bishop criteria referenced in the publication by Coiffier et al (2008) (see Section 11.14).

The investigator is responsible for ensuring that all adverse events observed by the investigator or reported by the subject that occur after first dose of investigational product(s)/study treatment/protocol-required therapies through the safety follow-up visit (30 [+3] days after the last dose of investigational product/study treatment/protocol-required therapies) are reported using the Events CRF.

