8.2.4.1.2 Serious Adverse Events

The investigator is responsible for ensuring that all serious adverse events observed by the investigator or reported by the subject that occur after signing of the informed

consent through the **LTFU visit or End of Study Visit (whichever occurs later)** are reported using the **Events** CRF.

All serious adverse events will be collected, recorded, and reported to the sponsor or designee within 24 hours of the investigator's knowledge of the event, as indicated in Section 11.4. The investigator will submit any updated serious adverse event data to the sponsor within 24 hours of it being available.

The criteria for grade 4 in the CTCAE grading scale differs from the regulatory criteria for serious adverse events. It is left to the investigator's judgment to report these grade 4 abnormalities as serious adverse events.

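### A serious AE judged related to AMG 910 but starting more than 30 days after the last dose cannot count as treatment-related, although the protocol collects it

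*SAP*

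**What the plan says.** **Definitions (SAP section 5).** An AE is treatment-emergent if it starts on or after the first dose and "up to and including 30 days after the last IP dose date". The anchor is the final administration: "The last IP date for each subject is defined as the latest date IP administered". The next definition builds on this one: "A treatment-related AE is any treatment-emergent AE that per investigator review has a reasonable possibility of being caused by AMG 910". The SAP gives no other definition of a treatment-related event. Its definition of a serious AE carries no time window.

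**Endpoint (protocol section 3, SAP section 2.1).** Treatment-related AEs are a primary endpoint, listed separately from treatment-emergent AEs.

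**Collection (protocol).** Section 8.2.4.1.1 collects AEs "through the safety follow-up visit (30 [+3] days after the last dose of" study treatment. Section 8.2.4.1.2 collects serious AEs from consent to a later point: "LTFU visit or End of Study Visit (whichever occurs later"). The synopsis runs long-term follow-up "up to 2 years from the first dose of AMG 910" and names serious AEs among the items assessed. Appendix 4 (section 11.4) requires the investigator to assess causality for every AE and serious AE. It leaves the definition of treatment-emergent to the SAP, and sets no time limit on relatedness.

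**Tables (SAP section 9.6.2).** Separate tables are planned for treatment-related AEs, all serious AEs, related serious AEs and fatal AEs. The section does not say whether the serious, related-serious and fatal tables are limited to treatment-emergent events. SAP section 10 declares no changes from the protocol analyses.

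**The concern.** A treatment-emergent window is a timing rule that stands in for causality when causality is uncertain. Here it is applied to events for which the investigator has already given a causal judgement, and it overrides that judgement once 30 days have passed.

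This is a first-in-human study of a half-life-extended T-cell engager with expected injury to the stomach mucosa (protocol section 2.3). Protocol section 6.2.1.1.2 itself foresees late-onset AEs and late endoscopic findings. A late serious event attributed to the drug would be recorded, assessed as related and then left out of the endpoint meant to count it. Where the rule has an effect, that effect is always to lower the related-event count.

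**Working it through.** The plan states no figure that can be reproduced on this point. The check compares definitions and then counts days.

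**1. Does the exclusion follow from the text?** Treatment-related requires treatment-emergent. Treatment-emergent requires onset no later than last dose + 30 days. So a serious AE with onset on day 31 or later after the last dose is not treatment-related, whatever the causality field says.

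**2. Will such events be in the database?** Yes, if they occur. Protocol section 8.2.4.1.2, the synopsis and the Schedule of Activities (continual serious-AE review) all have them collected. SAP section 7.1 merges the primary analysis into the final one, and section 7.2 times that analysis after all subjects have ended the study.

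**3. How much of the collection period is uncovered?** Inputs: 28-day cycles; treatment-free breaks after cycles 2 and 4 of 14 days, extendable to 21 (protocol section 4.1); last planned dose on cycle 6 day 22; follow-up to 2 years from first dose, taken as 730 days.

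- Cycle 6 day 1 = 1 + 2×28 + b + 2×28 + b + 28, where b is the break length
- Last dose day L = cycle 6 day 1 + 21
- Window closes on day L + 30
- Uncovered days = 730 − (L + 30)

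| Subject | Last dose (day) | Window closes (day) | Uncovered days | Share of 730 |
|---|---|---|---|---|
| Six cycles, 14-day breaks | 169 + 21 = 190 | 220 | 510 | 70% |
| Six cycles, 21-day breaks | 183 + 21 = 204 | 234 | 496 | 68% |
| Last dose on day 22 | 22 | 52 | 678 | 93% |
| Single dose on day 1 | 1 | 31 | 699 | 96% |

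These are planned maxima for a subject who survives and stays in follow-up. Treatment beyond cycle 6 moves the last dose later and shrinks the gap.

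**4. Which outputs are affected?**

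| Output | Late related serious AE |
|---|---|
| Treatment-related AEs | Excluded by definition |
| Related serious AEs | Unclear: no window stated, but the only definition of related in the SAP has one |
| All serious AEs; fatal AEs | May still appear: no window stated |

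**5. What could one such event change?** Incidence is counted per subject, so the event moves a row only if that subject is not already counted there. If so, one subject is 1/3 = 33 or 1/4 = 25 percentage points in a cohort of 3 or 4, and 1/36 = 2.8 points in the expansion cohort.

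**The case against.** The strongest reply is that this is an analysis choice open to the SAP. The protocol leaves the treatment-emergent definition to the SAP, never defines treatment-related without a window, and times the primary safety analysis by the opportunity for six cycles, not by 2 years (section 9.4.1.2). A fixed 30-day window is uniform across subjects. Safety decisions do not depend on it: dose-limiting toxicities have their own window, the dose level review team may act on late-onset events, and serious AEs are reported within 24 hours. All of this stands, so the point is not a contradiction of the protocol and not a gap in subject protection. It does not explain why an event already judged related should be classified as not related.

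A reader might infer more than the documents support:

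- **That late related serious AEs vanish from the report.** The all-serious and fatal tables have no stated window, so they may still appear there.
- **That long-term follow-up exists mainly to find them.** Protocol section 8.1.4 and the SAP's own definition give its purpose as survival and subsequent therapy. The synopsis adds serious AEs as one item of three. The visit intended for delayed AEs is the safety follow-up: "the subject must return for a safety follow-up visit at least 30 (+3) days after the last dose of AMG 910".
- **That the comparison is 30 days against 2 years.** The first runs from the last dose and the second from the first dose. The day count above puts both on one scale.
- **That related-event rates are in fact biased, by 25 to 33 points.** The documents give no rate of late serious AEs, and a shift of that size needs a cohort of 3 or 4 and a subject not otherwise counted in that row.
- **That the treatment-emergent cut-off should move to the safety visit.** AEs starting on days 31 to 33 can be collected and fall outside the window. However, that is at most three days, and a cut-off tied to a variable visit date gives up uniformity for negligible gain.

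**Conclusion.** The point holds in a limited form. As defined in SAP section 5, a serious AE starting more than 30 days after the last dose and judged caused by AMG 910 cannot enter the treatment-related AE endpoint, and it may be left out of the related-serious-AE table.

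For six-cycle completers the uncovered part of planned serious-AE collection is about 68% to 70% (496 to 510 of 730 days). It is larger for subjects who stop early. This assumes full 2-year follow-up from first dose. SAP section 7.1 states that the sponsor ended the study early, so actual follow-up may be shorter. The number of affected events cannot be derived from the documents and may be zero. This is a misclassification rule to correct, not evidence of a wrong result.

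**What to change.** In SAP section 5, leave the 30-day treatment-emergent window as it is. Extend the treatment-related definition to add any serious AE starting on or after the first dose that the investigator judges related to AMG 910, regardless of time since the last dose. In section 9.6.2, state that the related-AE and related-serious-AE tables include these events through end of study, and flag those with onset more than 30 days after the last dose.

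The cost is a few sentences and one derivation flag, with no new data collection. Related-event rates may come out slightly higher. Ascertainment also becomes uneven: after the safety follow-up visit only serious AEs are collected, possibly after other anticancer therapy has begun, since protocol section 6.1.7 bars such therapy only until safety follow-up. The flag makes those events visible, so rates can be read with and without them.
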